AUC	Area Under the Curve
bid	bis in diem/twice a day
CSR	Clinical Study report
CTC	Common Toxicity Criteria
CTCAE	Common Terminology Criteria for Adverse Events
DMC	Data Monitoring Committee
FAS	Full Analysis Set
eCRF	Electronic Case Report Form
IVR	Interactive Voice Response
IWR	Interactive Web Response
MedDRA	Medical Dictionary for Drug Regulatory Affairs
NCI	National Cancer Institute
o.d.	Once Daily
OS	Overall Survival
PFS	Progression-Free Survival
PK	Pharmacokinetics
PPS	Per-Protocol Set
PRO	Patient-reported Outcomes
qd	Quaque die / once a day
QoL	Quality of Life
RAP	Report and Analysis Process
RECIST	Response Evaluation Criteria in Solid Tumors
SAP	Statistical Analysis Plan
SOC	System Organ Class
TFLs	Tables, Figures, Listings
WHO	World Health Organization

1 Introduction

This document describes the detailed statistical analysis plan for final CSR for study LEE011X2102. The final CSR will be written after the final database lock.

The statistical analyses which are covered in the RAP Module 3 for the primary CSR are not repeated within this document. Refer to [REDACTED]

[REDACTED]

All changes to the planned analysis described in this document required before or after database lock will be made through an amendment or addendum, respectively. Note that obvious corrections will be made at the time of analysis to address minor formatting or spelling mistakes present in the TFL shells document without the need to amend.

The SAP, TFL shells and PDS documents may also serve as a reference for the creation of any outputs required outside of the CSR, e.g., PSUR/DSUR, MTD/RDE declaration, IB updates, abstracts, posters, presentations, manuscripts, health authority requests and management updates.

1.1 Study design

See the primary CSR RAP Module 3.

1.2 Study objectives and endpoints

Please see the primary CSR RAP Module 3.

2 Statistical methods

2.1 Data analysis general information

See the primary CSR RAP Module 3.

2.1.1 General definitions

See the primary CSR RAP Module 3.

2.2 Analysis sets

See the primary CSR RAP Module 3.

2.2.1 Subgroup of interest

See the primary CSR RAP Module 3.

2.3 Patient disposition, demographics and other baseline characteristics

Background, baseline and demographic characteristics including age, gender, race, ethnicity, height, weight, body surface area (BSA), body mass index (BMI), Karnofsky/Lansky performance status, etc., are listed individually by patient and summarized by treatment for patients in the FAS.

BMI and BSA (Gehan and Georage formulae) are calculated using the following formulas:

- $BMI [kg/m^2] = weight[kg] / (height[m]**2)$
- $BSA [m^2] = 234.94*(height[cm]**0.422)*(weight[kg]**0.515)/10000$

BMI may be summarized by categories as appropriate. It is acceptable for the BSA to be calculated up to 7 days in advance of Day 1. Dose adjustments for changes in BSA in subsequent cycles are made as per standard site practice (e.g., if the BSA changes by $\pm 10\%$ from the previous dose calculation).

Performance status is scored using the Karnofsky (for patients > 16 years old) or Lansky (for patients ≤ 16 years old) performance scales (Protocol [Appendix 4](#) and 5).

For patients that have their 17th birthday during the study, performance status will continue to be assessed by the Lansky scale, in order to preserve continuity.

2.3.1 Patient disposition

The following patient disposition information are listed and summarized by treatment for all patients in FAS at the time of final database lock:

- Enrolled patients who remained on treatment or discontinued treatment
- Primary reasons for EOT based on EOT CRF
- Study evaluation completion after EOT:
 - Patients who are either no longer being followed up for study evaluation or who continued to be followed for study evaluation based on EOT CRF
 - Primary reason for study evaluation completion based on Study Evaluation Completion CRF.

2.4 Treatments (study treatment, rescue medication, concomitant therapies, compliance)

2.4.1 Study treatment / compliance

Duration of exposure to study drug is categorized into time intervals in days (≤ 56 , $57-\leq 84$, $85-\leq 140$, and ≥ 141) and in cycles (≤ 1 , $2 - \leq 3$, $4 - \leq 5$, ≥ 6), frequency counts and percentages are summarized for the number of patients in each interval.

Duration of exposure to study drug by treatment is listed.

The safety set is used for all summaries tables and listings of study drug.

See the primary CSR RAP Module 3 for more detailed definitions.

2.4.2 Prior, concomitant and post therapies

No analysis of prior, concomitant or post therapy will be performed for the final CSR.

2.5 Analysis of the primary objective

The primary objective of the dose-escalation part was to determine the MTD of LEE011 when administered as a single agent orally to patients aged 12 months to 21 years old with malignant rhabdoid tumors and neuroblastoma. The MTD/RDE of LEE011 was determined prior to halted enrollment.

No analysis related to MTD will be performed for the final CSR as this analysis was fully covered in the primary CSR.

2.5.1 Primary endpoint

See the primary CSR RAP Module 3.

2.5.2 Statistical hypothesis, model, and method of analysis

See the primary CSR RAP Module 3.

2.5.3 Handling of missing values/censoring/discontinuations

See the primary CSR RAP Module 3.

2.5.4 Supportive analyses

The MTD was to be further evaluated for preliminary anti-tumor activity and overall tolerability during the dose-expansion part of the trial. Due to halted enrollment, this analysis will not be performed.

2.6 Analysis of the key secondary objective

No key secondary objective is defined.

2.7 Analysis of secondary efficacy objective(s)

No other secondary efficacy objectives will be analyzed for the final CSR.

2.8 Safety analyses

2.8.1 Adverse events (AEs)

AEs are coded using the Medical Dictionary for Regulatory Activities (MedDRA) terminology. Although CTCAE version 4.03 grading is by definition a 5-point scale generally corresponding to mild, moderate, severe, life threatening and death, CTCAE grade 5 (death) is not used since this information was collected at the “End of Treatment” and “Study evaluation completion” pages.

Summary tables for AEs include only AEs that started or worsened during the on-treatment period, the **treatment-emergent** AEs. AEs, SAEs, and all deaths (on treatment and post treatment) are tabulated by primary system organ class, preferred term, severity and treatment.

Additional summaries based on causality, study drug discontinuation or study drug interruptions are produced.

All AEs collected in the AE (e)CRF page will be listed along with the information collected on those AEs e.g. AE relationship to study drug, AE outcome etc.

Listing and summaries are produced according to the following rules:

- Patients reporting and experiencing multiple occurrences of a specific AE have occurrences listed but are counted only once in the appropriate event category/class and according to the worst observed grade within summary tables.
- AEs are summarized by presenting the number and percentage of patients having at least one AE sorted by descending frequency then alphabetically (by system organ class and preferred term).

Analysis for clinicaltrials.gov and EudraCT

For the legal requirements of clinicaltrials.gov and EudraCT, two required tables on treatment emergent adverse events which are not serious adverse events with an incidence greater than and equal to 5% and on treatment emergent serious adverse events and SAE suspected to be related to study treatment will be provided by system organ class and preferred term on the safety set population.

If for a same patient, several consecutive AEs (irrespective of study treatment causality, seriousness and severity) occurred with the same SOC and PT:

- a single occurrence will be counted if there is ≤ 1 day gap between the end date of the preceding AE and the start date of the consecutive AE
- more than one occurrence will be counted if there is > 1 day gap between the end date of the preceding AE and the start date of the consecutive AE

For occurrence, the presence of at least one SAE / SAE suspected to be related to study treatment / non SAE has to be checked in a block e.g., among AE's in a ≤ 1 day gap block, if at least one SAE is occurring, then one occurrence is calculated for that SAE.

The number of deaths resulting from SAEs suspected to be related to study treatment and SAEs irrespective of study treatment relationship will be provided by SOC and PT.

2.8.1.1 Adverse events of special interest / grouping of AEs

An adverse event of special interest is a grouping of adverse events that are of scientific and medical concern specific to compound LEE011. These groupings are defined using MedDRA terms, SMQs (standardized MedDRA queries), HGLTs (high level group terms), HLT (high level terms) and PTs (preferred terms). Customized SMQs (Novartis MedDRA queries, NMQ) may also be used. A NMQ is a customized group of search terms which defines a medical concept for which there is no official SMQ available or the available SMQ does not completely fit the need. It may include a combination of single terms and/or an existing SMQ, narrow or broad. For each specified AESI, number and percentage of subjects with at least one event of the AESI occurring during on-treatment period will be summarized.

Summaries of these AESIs will be provided by treatment, (specifying grade, SAE, relationship, leading to treatment discontinuation, leading to dose adjustment/interruption, fatal outcome, etc.).

A listing of all grouping levels down to the MedDRA preferred terms used to define each AESI will be generated.

2.8.2 Deaths

Summary of all deaths will be produced by treatment, system organ class and preferred term. All deaths will be listed for the full analysis set, on-treatment deaths will be flagged.

2.8.3 Laboratory data

Summary of notable hepatic laboratory values will be produced by treatment. Liver function test values will be listed. No other laboratory data will be analyzed for the final CSR.

2.8.4 Other safety data

2.8.4.1 ECG and cardiac imaging data

No ECG and cardiac imaging data will be analyzed for the final CSR.

2.8.4.2 Vital signs

No vital signs data will be analyzed for the final CSR.

2.9 Pharmacokinetic endpoints

No Pharmacokinetic data will be analyzed for the final CSR.

2.10 PD and PK/PD analyses

No PD data will be analyzed for the final CSR.

2.11 Patient-reported outcomes

No patient-reported outcomes will be analyzed for the final CSR.

2.12 Biomarkers

No biomarker data will be analyzed for the final CSR.

2.13 Other Exploratory analyses

No other exploratory analyses will be executed for the final CSR.

2.14 Interim analysis

See the primary CSR RAP Module 3.

3 Sample size calculation

See the primary CSR RAP Module 3.

4 Change to protocol specified analyses

- Due to halted enrollment, all analyses are performed for the dose-escalation part only.
- The analysis of adverse events of special interest is added.
- For the final CSR only limited demographic, disposition, exposure and safety data will be analysed.

5 Appendix

This appendix gives details about statistical methods in addition to the report text.

5.1 Imputation rules

As a general rule, when a date is recorded as a partial date, the missing day is imputed to the 15th of the month (e.g., DEC2007 imputed to 15DEC2007), and if the day and month are both missing then to July 1st of that year (e.g., 2007 imputed to 01JUL2007). Such imputed data are flagged in the listings.

For computation of time intervals (e.g. elapse time between initial diagnosis to first recurrence/relapse), if the imputation rule leads to a negative value, time interval should be set to missing.

Continuing events (e.g. AEs) are summarized using the data cut-off date as the date of completion, with an indication within listings that the event is continuing. For patients who discontinue the study with ongoing events, the discontinuation date is used as the completion date of the event with the appropriate censoring.

Other missing data will simply be noted as missing on appropriate tables/listings

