10.5.2 Safety evaluation

10.5.2.1 Analysis set and grouping for the analyses

The overall observation period will be divided into three mutually exclusive segments:

1. Pre-treatment period: from day of patient's informed consent to the day before first dose of study medication.
2. On-treatment period: from day of first dose of study medication to 30 days after last dose of study medication.
3. Post-treatment period: starting at day 31 after last dose of study medication.

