5.1.2 AE date imputation

See [Section 5.1](#)

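### The SAP's partial-date rule for AE starts is not checked against the on-treatment limits or the AE's end date, so some on-treatment AEs can drop out of the AE summary tables (minor)

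*SAP*

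**What the plan says.** The SAP section headed "5.1.2 AE date imputation" contains only a reference back to Section 5.1. That section, introduced as a general rule, says that "when a date is recorded as a partial date, the missing day is imputed to the 15th of the month" and "if the day and month are both missing then to July 1st of that year". Imputed dates are flagged in listings. The one plausibility safeguard concerns computed intervals: "if the imputation rule leads to a negative value, time interval should be set to missing".

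The AE tables depend on the resulting date. SAP 2.8.1: "Summary tables for AEs include only AEs that started or worsened during the on-treatment period". SAP 2.8.1.1, for events of special interest: "number and percentage of subjects with at least one event of the AESI occurring during on-treatment period will be summarized". The registry tables in SAP 2.8.1 use treatment-emergent events, and the one for non-serious AEs is limited to those "with an incidence greater than and equal to 5" per cent. Protocol 10.5.2.1 sets the limits: "On-treatment period: from day of first dose of study medication to 30 days after last dose of study medication".

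**The concern.** The 15th of the month is a neutral midpoint for computing durations. Here, however, the imputed date also decides whether an AE is counted at all. When first dose falls after the 15th, an on-treatment AE known only by that month is dated before treatment. When the period ends before the 15th, an AE known only by that last month is dated after it. Setting a negative interval to missing changes neither the imputed start nor the period in which the AE falls.

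According to SAP section 4, the final CSR analyses only limited demographic, disposition, exposure and safety data, so the AE tables are much of its content. Losing on-treatment events is the non-conservative direction for a safety table. The denominators are also small: dose escalation only (SAP section 4), planned at about 28 patients (Protocol 10.8).

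**Working it through.** **The rule itself.** SAP 5.1 gives two examples, DEC2007 to 15DEC2007 and 2007 to 01JUL2007. Coding the rule as written reproduces both.

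**Worked cases (assumed dates).**
- First dose 20 May, start recorded as MAY: imputed 15 May, hence pre-treatment and out of the tables.
- Period ends 10 May, start recorded as MAY: imputed 15 May, hence post-treatment and out.
- AE end 8 May, start recorded as MAY: imputed start 15 May, after the AE's own end.

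**Share misclassed, start day missing.** Assumptions: first-dose dates uniform over four calendar years (2013 to 2016, 1,461 days; the years only set the calendar) and AE onset uniform over the on-treatment period. Last dose is taken as day 21, 49 or 161, the last dosing day of cycles 1, 2 and 6 on the 21-days-on, 7-days-off schedule. The on-treatment period is then 21+30 = 51, 49+30 = 79 or 161+30 = 191 days.

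*Moved before first dose.* If first dose is on day k of a month of m days, with k at least 16, the m−k+1 remaining days of that month are imputed too early. Summed over k = 16 to m this is (m−15)(m−14)/2, which is 136, 120, 105 and 91 for months of 31, 30, 29 and 28 days. Four years give 28×136 + 16×120 + 1×105 + 3×91 = 6,106 onset days, or 6,106/1,461 = 4.18 per patient.

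*Moved past the period.* If the period ends on day k of a month, with k at most 14, the first k days of that month are imputed too late. Summed over k = 1 to 14 this is 105 per month: 48×105 = 5,040, or 5,040/1,461 = 3.45 per patient.

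Dividing by the length of the period:

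| Last dose | Before first dose | After period | Total |
|---|---|---|---|
| Day 21 (51 days) | 8.2% | 6.8% | 15.0% |
| Day 49 (79 days) | 5.3% | 4.4% | 9.7% |
| Day 161 (191 days) | 2.2% | 1.8% | 4.0% |

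A full day-by-day enumeration gives the same figures.

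**Share of all on-treatment AEs.** The proportion of AEs with a missing start day is not in the documents. If it were 1% to 10% (assumption), the loss would run from 1% × 4.0% = 0.04% to 10% × 15.0% = 1.5%. The upper end also requires every patient to stop at day 21.

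**Start after end.** With a complete end date, the imputed start falls after it for 39.4%, 26.3% and 3.3% of day-missing AEs lasting 3, 7 and 14 days.

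**What one patient is worth.** 1/28 = 3.6% and 2/28 = 7.1%. For any total from 21 to 40 patients, one patient is below 5% and two reach it, so one lost patient can remove a preferred term from the non-serious registry table.

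**The case against.** The strongest reply is that no affected record is shown. Protocol 8.1.1 has AEs sought at each visit with start and end dates, Protocol 9.3 has automatic validation checks, and Protocol 9.4 has missing values queried. Partial dates should therefore be few. This stands, and it keeps the point minor.

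The consequences are also bounded. Every AE is listed with imputed dates flagged. Events that worsened on treatment still count. SAP 2.8.1 tabulates all deaths, on and post treatment. The 5% cut-off applies only to the non-serious table. A cell changes only if the patient has no other qualifying occurrence or the lost event carried the worst grade. The start-after-end shares are not tied to any particular planned table. All of this stands.

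Two replies do not remove the point. SAP 5.1 is worded as a general rule, which allows exceptions, but none is written for AEs. Much of the SAP defers to the primary CSR RAP Module 3, which is not available here and might hold a rule; but 5.1.2 cites 5.1, not that module.

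A reader might infer that on-treatment AEs have in fact been lost, or that the safety results are materially understated. The documents do not support that, because they give no count of partial dates and the 15th rule errs both ways: 16.4% of day-missing AEs from the 21 days before first dose are now dated on treatment. A reader might also seize on starts recorded by year only, where the same enumeration gives 86.0%, 78.4% and 47.8% misclassed. Such records should be rare, and those shares should carry no weight.

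**Conclusion.** The rule is wrong as written, but minor. Followed literally, SAP 5.1.2 can class a true on-treatment AE as pre- or post-treatment, and can date its start after its own recorded end. The share is about 15.0%, 9.7% or 4.0% of on-treatment AEs with the start day missing, for last dose on day 21, 49 or 161, with uniform first-dose and onset dates assumed. The number of such AEs is unknown and probably small, so the effect on the final tables is probably very small. No MTD result is touched, since SAP 2.5 leaves the MTD analysis to the primary CSR.

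**What to change.** In SAP 5.1.2, after applying 5.1, add three checks in this order:

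1. If the imputed start is after a complete AE end date, set it to that end date.
2. If the imputed start is before first dose, the recorded part of the start is compatible with onset on or after first dose, and the recorded part of the end date does not show that the AE ended before first dose, set the start to the first-dose date.
3. If the imputed start is after last dose plus 30 days, the recorded part of the start is compatible with on-treatment onset, and the recorded part of the end date does not show that the AE ended before first dose, set the start to the last on-treatment day, or to the complete AE end date if that is earlier.

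Use recorded, not imputed, end-date parts in these tests. With first dose 20 May and both start and end recorded only as MAY, an imputed end of 15 May would wrongly show the AE as finished before treatment. The end-date condition in check 3 is needed too. With a year-only start, an end recorded as February, first dose 20 March and a period ending 10 May, the imputed 1 July would otherwise be moved to 10 May and a pre-treatment AE counted. Keep the listing flag. If RAP Module 3 already holds such a rule, cite it in 5.1.2 instead.

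The cost is a few lines in the SAP and the AE program. In the day-missing enumeration, no on-treatment AE is then lost, whether its end date is complete, day-missing or absent. This assumes that recorded date parts are right and that first- and last-dose dates are complete.

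The price is more ambiguous events counted as on treatment, which is the cautious direction for safety tables:
- For day-missing AEs from the 21 days before first dose, the share counted is 9.1%, 25.3% and 47.7% with a complete end date (3-, 7- and 14-day AEs), and up to 63.9% with the end day missing or no end date, against 16.4% now.
- For day-missing AEs starting 1 to 30 days after the period, it is 49.1% against 13.9% now. Few should exist, since Protocol 8.2.2 limits SAE reporting after 30 days to suspected related events.

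Some counts may differ from the primary CSR and would need a footnote.

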5.1.1 Study drug

The study drug and study treatment refer to the Novartis investigational drug LEE011, an orally bioavailable small molecule inhibitor of CDK4/6.

5.1.2 AE date imputation

See [Section 5.1](#)

5.1.3 Concomitant medication date imputation

See [Section 5.1](#)

5.1.3.1 Prior therapies date imputation

See [Section 5.1](#)

5.1.3.2 Post therapies date imputation

See [Section 5.1](#)

5.1.3.3 Other imputations

5.2 AEs coding/grading

AEs are coded using the Medical Dictionary for Regulatory Activities (MedDRA) terminology. Although CTCAE version 4.03 grading is by definition a 5-point scale generally corresponding to mild, moderate, severe, life threatening and death, CTCAE grade 5 (death) is not used since this information was collected at the “End of Treatment” and “Study evaluation completion” pages.

5.3 Laboratory parameters derivations

All laboratory values are converted into SI units when applicable and the severity grade calculated using CTCAE, version 4.03 unless otherwise indicated. A severity grade of 0 is assigned when the value is within normal limits. In the case when a local laboratory normal range overlaps into the higher (i.e., non-zero) CTC grade, the laboratory value is still considered within normal limits and assigned a CTC grade of zero.

5.4 Statistical models

5.4.1 Primary analysis

See the primary CSR RAP Module 3.

An adaptive BLRM with two parameters guided by the EWOC principle is used to make dose recommendations and estimate the MTD/ RDE during the study. The model is fitted on the Cycle 1 DLT data (i.e. absence or presence of DLT).

The adaptive BLRM model is fitted on the dose-limiting data (i.e. absence or presence of DLT) accumulated in Cycle 1 throughout the dose-escalation part (and possibly during the dose-expansion part), for modeling the dose-DLT relationship of LEE011.

The DLT relationship in the dose-escalation part of the study is described by the following Bayesian logistic regression model:

$$\text{logit}(\pi_{(d)}) = \log(\alpha) + \beta \log(d/d^*), \quad \alpha > 0, \beta > 0$$

where $\text{logit}(\pi_{(d)}) = \ln(\pi_{(d)}/(1-\pi_{(d)}))$, and $\pi_{(d)}$ is the probability of a DLT at dose d .

Doses are rescaled as d/d^* with reference dose of $d^* = 580 \text{ mg/m}^2$. As a consequence α is equal to the odds of the probability of toxicity at d^* . Note that for a dose equal to zero, the probability of toxicity is zero.

If a different dosing schedule is considered, a Bayesian Meta-analytic approach is used to take into account historical data collected for the initially planned schedule in the actual study, in order to derive an informative prior estimation of the dose-toxicity relationship for the new dosing regimen. This informative prior is combined with DLT data for the new dosing regimen using a two-parameter BLRM. After patients in each cohort have completed at least one cycle of LEE011 treatment, the prior distribution is updated with the cumulated DLT data from Cycle 1. Posterior probabilities for the rate of DLT are summarized; the recommendation for the next dose level is based on these probabilities.

[REDACTED]

Prior specifications

The Bayesian approach requires the specification of prior distributions for the model parameters. All information currently available about the dose-DLT relationship of LEE011 was summarized in a prior distribution.

[REDACTED]

[REDACTED]

[REDACTED]

Operating characteristics of this model and the escalation recommendations for some particular situations are provided in Protocol Appendix 7.

